**Optional remote daily symptom reporting:**

\*Due to application development barriers, the study team had to close version 1 of the *MyPainPal* app before version 2 was fully developed and functional. So, participants recruited after April 4th, 2023, were not offered the optional remote daily symptom reporting.

Patients will also be given the option of completing daily pain assessments using a smartphone application developed by [name] and the study team. *MyPainPal*, is an Android and iPhone-compatible smartphone app that hosts patients analgesic and laxative medications (inputted by the study assistant), it delivers symptom surveys, and provides tailored psychoeducation relevant to cancer pain. The app will send a reminder to complete a brief symptom survey twice per week which will include the following 6 items, which are estimated to take no longer than 5 minutes to complete.

Assessments used for this study can be found in appendix C.

- Pain severity (4 items): patients will rate their pain at its least, worst, and average over the past 24 hours on a scale from 0-10, and their pain at present, and whether their pain is acceptable to them
- Opioid use: patients indicate the number of doses of breakthrough opioids they used in the last 24 hours, and they are asked how much relief it provided
- Pain interference (3 items): patients will rate the extent to which pain interferes with general activity (scale, 0-10) sleep, and mood also derived from the BPI-SF
- Constipation: including last bowel movement and laxatives taken.

Survey results from *MyPainPal* are visible immediately within a password-protected, HIPPA-compliant research portal. The study assistant will monitor this portal daily. For any severe symptoms, the study assistant will notify the patients' care team within that business day. Results from the symptom surveys will be used to algorithmically generate an end of survey summary screen on the patients' app after completing the survey, and if needed, recommend the patient to reach out to their care team regarding

PROTOCOL TITLE: Randomized Clinical Trial of Early Intervention Pain Management for Patients with Advanced Cancers  
Version 4.0, [October 27, 2023]

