## 7. Description of research procedures being performed

### 7.1. Survey Assessments

Patient will complete surveys at baseline (window 0-2 weeks), 2 months (window 7-13 weeks), and 4 months (window 15-19 weeks) (see appendices DA, DB and DC respectively).

PROTOCOL TITLE: Randomized Clinical Trial of Early Intervention Pain Management for Patients with Advanced Cancers  
Version 4.0, [October 27, 2023]

The surveys can be completed remotely through a link to a Partners Healthcare compliant electronic survey system (e.g. REDCap), over the phone with the RA, over Zoom with the RA; or in person with pen and paper or on a tablet. The Baseline survey will assess socio-demographics pain severity/interference, opioid use, symptoms, and quality of life, with metrics shown in Table 3. of study survey will largely replicate the baseline survey, additionally, patients will rate their satisfaction with their pain management care. See appendix DA for the Baseline survey items

Patients recruited before April 4th, 2023 were also be given the option of completing daily pain assessments using a smartphone application. *MyPainPal*, developed by study PI, [name], is an Android and iPhone-compatible smartphone app that delivers symptom surveys and tailored cancer pain psychoeducation geared toward advanced cancer patients using opioids. Patients will be pushed twice weekly surveys, optional for study participation, and are included for exploratory longitudinal analyses to examine the pre-post effects of specific pain interventions.

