### 7.3. Data Collection:

Three survey assessments (at baseline, 2-months, and 4-months) will assess future outcomes and covariates needed to plan a future randomized clinical trial, including patients' pain, functional wellbeing, and quality of life. The daily symptom reporting using a smartphone platform will enable

PROTOCOL TITLE: Randomized Clinical Trial of Early Intervention Pain Management for Patients with Advanced Cancers  
Version 4.0, [October 27, 2023]

exploratory longitudinal analyses of response to pain procedures. Structured chart abstractions will assess treatment compliance, opioid prescribing, changes in pain management, and healthcare utilization (i.e. hospitalization, ED visits).

Survey assessments: Patient will complete surveys at baseline, 2 months and 4 months. We anticipate pre-post differences in pain severity scores from baseline to 4 months to be our future primary outcome in a randomized clinical trial. 4 months is a relevant timeframe, because we anticipate it will be sufficient for a patient to be evaluated and treated with at least one interventional pain procedure, and any needed secondary procedures if response is insufficient.

The baseline survey will assess socio-demographics, characteristics and severity of pain, symptom burden and quality of life, and psychological characteristics known to influence pain (e.g. pain catastrophizing, perceived stress, anxiety, depression, sleep). Subsequent surveys will be brief and will focus on pain severity, functional interference, and quality of life.

7.3.1. Structured chart abstractions: A study assistant will abstract clinical characteristics at baseline (e.g. tumor type and location of metastases, date of diagnosis, current treatment). At the end of study, the RA will also conduct a detailed abstraction to evaluate the following (see appendices BA and BB):

- Any interventional pain management procedures, and dates of procedures
- Opioid doses (MMEDs) and dates of medication changes
- Unplanned and planned hospitalizations for pain
- Emergency department visits for pain
- Survival (which will be augmented by the National Death Index, which is integrated into the DFCI research database OnCORE through an existing process)

7.3.2. Smartphone based symptom reporting: \* As described in section 6.2, this is not applicable to patients recruited to the study after April 4th, 2023.

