Patients will be given the option to use a secure smartphone application to report on daily symptoms and to track their objective activity levels. Patients will be incentivized \$5 for each week that they complete at least 2 daily assessments.

*MyPainPal* is a secure smartphone application developed, validated, and optimized by [name]. It is fully HIPPA-compliant with all relevant security standards needed to protect health information, and has demonstrated to have high patient acceptability. The application can be downloaded for free through the Apple Store and Google Play. All data are saved on a secure encrypted password-protected server. The application hosts patients analgesic and laxative medications (including dose and frequency), linked to comprehensive medication education. Patients are pushed a brief daily survey which assesses pain severity and interference from the BPI, mood (use of PRN opioids in the past 24 hours, pain relief, constipation and laxative use. Patients receive custom educational pearls in response to each daily survey spanning medication teaching, psychoeducation and skills training (e.g. activity pacing). The application also includes an educational library covering psychological and medical pain management strategies. See appendix C for screen shots of the application. The advantage of this approach is that the brief daily assessments (pain severity, interference) will overlap with the primary/secondary outcome assessments and it will be used to impute these outcomes should survey data be incomplete. Moreover, these will be rich data that will allow exploration of longitudinal outcomes, responses to specific interventions (e.g. procedures, opioid titration), and relationships between pain severity, interference and QOL.

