We will fit longitudinal data on pain (derived from the smartphone-based symptom reporting) with linear regressions to estimate the trajectories in pain and to explore the effect of the intervention on pain trajectories, adjusting for each participant's baseline measure. We will also explore the association of potentially moderating variables (e.g. opioid doses, specific interventions patients have for their pain) and clinical characteristics (e.g., stage) with on pain outcomes via linear probability models. These analyses are underpowered, but will be used to explore potentially meaningful differences and estimate a possible effect size and conduct sample size calculations for a future randomized clinical trial.

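### Section 9 fits repeated app pain scores by linear regression without stating how within-patient correlation is handled, and uses linear probability models for pain outcomes without naming a binary outcome

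*Combined protocol and SAP*

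**What the plan says.** Section 9 describes the app analysis in one sentence: "We will fit longitudinal data on pain (derived from the smartphone-based symptom reporting) with linear regressions to estimate the trajectories in pain". Its stated aims include "to explore the effect of the intervention on pain trajectories", and the participant's baseline value is the only covariate named. The next sentence relates moderators and clinical characteristics "on pain outcomes via linear probability models". Section 9 concedes that these analyses lack power, but will use them to look for differences worth pursuing and to help size a later randomised trial. Earlier in the section the significance level is set at 0.05.

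The app data are repeated measures by design. Section 6.2 states: "The app will send a reminder to complete a brief symptom survey twice per week". Section 7.1 describes "twice weekly surveys, optional for study participation, and are included for exploratory longitudinal analyses to examine the pre-post effects of specific pain interventions". Section 7.3 foresees "exploratory longitudinal analyses of response to pain procedures". Section 7.3.2 differs on frequency: "Patients are pushed a brief daily survey which assesses pain severity and interference from the BPI".

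Three other places bear on the point:
- Section 6.2 defines pain severity as the mean of BPI ratings on a 0-10 scale.
- Section 6.2 and the text under Table 2 make the app optional and limit it to participants recruited before April 4, 2023.
- Section 6.1 gives the design as single-arm.

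**The concern.** Records from one patient resemble each other, and patients differ in how their pain changes. An ordinary regression on pooled records treats each record as independent, so its standard errors and p-values do not reflect the number of patients. Nothing in the plan names a random effect, GEE, a clustered or robust standard error, or a two-stage per-patient fit. Section 9 does list cluster analyses among generic methods, but does not define them or tie them to the app data. Adjusting for baseline reduces the correlation without removing it.

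The moderator sentence has a different gap. A linear probability model is a regression of a 0/1 variable, and an analyst reading Section 9 cannot tell which variable that is.

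At stake are the exploratory p-values and intervals that would be used to pick out trends or subgroups for a later trial.

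**Working it through.** The plan gives no figure for these models, so there is none to reproduce. The check sizes the consequence if records are pooled.

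**Inputs from the documents.** Follow-up is 4 months (Section 5.1.2), about 17 weeks. At two surveys per week, a full responder gives 17 x 2 = 34 records. A daily schedule would give about 120. The 34 is used here because Sections 6.2 and 7.1 say twice weekly and the incentive in Section 7.3.2 requires only two assessments a week.

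**Assumptions, not in the documents.** There are 10 or 20 app users. Total SD is 2 points (variance 4). The intraclass correlation r is 0.3 to 0.7 before baseline adjustment. The SD of individual slopes is 0, 0.25 or 0.5 points per month. All true effects are zero.

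**Step 1: what baseline adjustment leaves.** With one baseline measure and exchangeable correlation, the residual correlation is r/(1+r): 0.3/1.3 = 0.23, 0.5/1.5 = 0.33, 0.7/1.7 = 0.41.

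**Step 2: time trend.** For 34 equally spaced records over 4 months, the sum of squared time deviations is S = 48.1 and the mean of squared time is 5.41. With within-patient variance 4(1-r) and slope SD s, the large-sample ratio of true to naive standard error is

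sqrt{ [4(1-r) + s²S] / [4(1-r) + 4r(1-r) + 5.41s²] }.

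At r = 0.5:
- s = 0: sqrt(2.00/3.00) = 0.82
- s = 0.25: sqrt(5.01/3.34) = 1.22
- s = 0.5: sqrt(14.02/4.35) = 1.80

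The corresponding type I error is 2[1 - Φ(1.96/ratio)], which is about 2%, 11% and 27%. Below 1 the test is conservative; above 1 it rejects too often.

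Simulations of pooled regression on baseline and time, with 10 or 20 users and r from 0.3 to 0.7, agree. Across separate sets of runs the rejection rates at 34 records were:

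| Slope SD (points per month) | Type I error, time trend |
|---|---|
| 0 | about 1-5% |
| 0.25 | 8-15% |
| 0.5 | 22-34% |

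A one-sample t-test on per-patient slopes held 4-6% in the same settings.

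**Step 3: other terms, if added.** For a patient-level term the design effect is 1 + 33 x r/(1+r). At adjusted correlations of 0.23 and 0.41 this is 8.6 and 14.6, so the naive standard error is too small by a factor of 2.9 to 3.8. Simulated type I error was 49-69%. For a before/after-procedure step received by half the users it was 43-65%. If all users had a procedure it was 4-8%, close to nominal.

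**Step 4: why a plain before/after comparison is not a remedy.** If a procedure falls at month T of 4, the mean record time is T/2 before it and (T+4)/2 after it, a gap of 2 months whatever T is. An underlying trend of 0.25 points per month therefore appears as a change of 0.25 x 2 = 0.5 points with no procedure effect. In simulation an unadjusted t-test on such differences rejected in 38-78% of runs.

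**Step 5: linear probability models.** Pain severity is a 0-10 mean (Section 6.2), and Section 9 analyses its pre-post difference by t-test. Two items could be binary: the app question on whether pain is acceptable (Section 6.2) and pain-related emergency visits (Section 9). Neither is tied to this model, and no responder cut-off is given.

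**The case against.** The strongest reply is that this is brevity in an exploratory paragraph rather than a wrong method. The plural form of regressions may mean one fit per patient, which is valid, and Section 9 already admits low power. This stands in part: the documents do not show that records will be pooled, only that the plan does not choose. Low power is nevertheless a different fault from a wrong standard error, which can create false signals.

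A reader might take the 43-69% error rates as the size of the problem. The documents do not support that. The app sentence names the trajectory and the baseline value; it names no patient-level term and specifies no procedure step. Moderators appear in the next sentence, which is not said to use repeated records. With one value per patient, clustering does not arise there.

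It is also fair that 34 records is a maximum. The app was optional and was not offered to participants recruited after April 4, 2023, so the number of users is unknown and may be small.

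Finally, a linear probability model fitted to the 0-10 score is numerically an ordinary linear regression. That part is a question of definition, and no numerical consequence is claimed for it.

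**Conclusion.** The point holds as a minor one. Section 9 leaves open how repeated app records are analysed. Under pooling, the test of the time trend ranges from conservative (about 1-5%) to clearly too liberal (22-34%), depending on slope variation that the documents do not give. The 43-69% range applies only if a patient-level term, or a procedure step received by only some users, is added. All these rates rest on the assumed number of users, SD, correlation and slope variation, and on full response. The linear probability models lack a named 0/1 outcome.

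A reader might infer that the effect size carried into the future trial is biased, or that the main results are unsafe. Neither follows. No bias in the pooled estimate was shown, and the feasibility benchmarks and the pre-post t-test on survey pain scores do not use these models. The phrase "to explore the effect of the intervention on pain trajectories" should likewise not be read as a treatment effect: with one arm it can only be change over time.

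**What to change.** In Section 9:

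1. Analyse the app scores with a linear mixed model: fixed effects for time and baseline, a participant random intercept, a random slope if it can be fitted, and small-sample degrees of freedom. If users are too few or the model does not converge, use a one-sample t-test on per-patient slopes. The simulations above checked this fallback; they did not include the mixed model.
2. Estimate any procedure effect in the same model, as a before/after term dated to the procedure, with time included. Do not use an unadjusted before/after t-test.
3. Replace the linear probability models by a linear model for the 0-10 score, or name the binary outcome and its cut-off.
4. Describe the result as uncontrolled change over time.

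The cost is a few sentences and a routine model. No new data are needed, since Section 7.3.1 already abstracts procedure dates. The downsides are wider intervals for patient-level terms and possible non-convergence with few app users.

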## **10. Data Specimen Banking**

This study does not involve any specimen collection/banking of any kind.

Personal health information will be collected as part of this study.

All data collected during this study will be stored and used for future research. Any personal identifiers will be removed so that the information cannot be linked back to a patient.

Investigators can request the data collected from this study for new research. Data may also be shared with outside non-profit academic investigators as well as with for-profit pharmaceutical investigators or commercial entities with whom Dana-Farber collaborates. Requests must be sent to the study chair ([name]) and must be approved by the Dana-Farber IRB prior to sharing.

The consent form informs the participant that data collected for this study may be used in the future.

By consenting, participants agree. Participants will not be asked to provide additional informed consent for the use of de-identified information in future research.

There is no scheduled date on which the information and data that is being used or shared for this research will be destroyed, because research is an ongoing process.

## **11. Data Management and Confidentiality**

DF/HCC uses a clinical trial management system (CTMS) called OnCore, which is managed by the Office of Data Quality (ODQ).

PROTOCOL TITLE: Randomized Clinical Trial of Early Intervention Pain Management for Patients with Advanced Cancers  
Version 4.0, [October 27, 2023]

Patient participants will sign consent and we will collect basic demographic information. Patient participants WILL be registered in OnCore. We will NOT collect each participant's initials and date of birth. We will enter summary/batch accrual information into Dana-Farber's CTMS OnCore.

**Data security:** PHI data will be collected using multiple the MGB instance of REDCap and MyPainPal, a smartphone-based application developed by [name] at DFCI, which is approved for use on protocol 18-504.

**REDCap:** For this study, data will be collected using the Partners instance of REDCap (redcap.partners.org). In collaboration with the Harvard Catalyst | The Harvard Clinical and Translational Science Center, REDCap (Research Electronic Data Capture) is a free, secure, HIPAA compliant web-based application hosted by Partners HealthCare Research Computing, Enterprise Research Infrastructure & Services (ERIS). Vanderbilt University, with collaboration from a consortium of academic and non-profit institutional partners, develops this software application for electronic collection and management of research and clinical study data. Data collection is customized for each study or clinical trial by the research team with guidance from ERIS REDCap administrators. REDCap is built around HIPAA guidelines and is 21 CFR Part 11 capable.

**MyPainPal App:** The final application will be HIPAA compliant and compliant with DFCI security and privacy standards

**To maximize data security, both REDCap and the MyPainPal App will employ:**

User Privileges. To ensure that users have access only to data and information that they are supposed to have within the application, user privileges are utilized within the software. Each user has their own account, and their user account will only have access to information that they themselves have created or to which administrators have granted them access.

Password-protection & Authentication. Both systems are password protected and implement authentication to validate the identity of end-users that log in to the system.

Auto-logout setting will automatically log a user out of the system if they have not had any activity (e.g. typing, moving the mouse) on their current web page for the set

amount of time. This prevents someone else from accessing their account and their data if they leave a workstation without properly logging out or closing their browser window.

Logging and Audit Trail. Both systems maintain built-in audit trails that log all user activity and all pages viewed by every user.

**Study specific procedure to maximize data security:**

Controlled access: The REDCap and *MyPainPal* app administrators will set up all user accounts so that each user only has access to their own relevant participant data.

Use of unique study ID numbers: REDCap automatically assigns unique study ID numbers to each new case.

Extensive training: All personnel involved in this study are required to complete and document completion of extensive protocol training. Furthermore, all research personnel are required to have valid certification of human subjects research training.

Quality control: The staff at Dana-Farber will be responsible for monitoring the data for completion, accuracy, and compliance.

**12. Provision to Monitor Data to Ensure the Safety of Subjects**

The study involves questionnaire-based assessments and symptom reporting and monitoring. The intervention is a care delivery intervention in which patients are referred to a specialty provider who will offer treatments and monitor the patient within the scope of their medical licensure, clinical expertise and practice. This study is not evaluating any investigational procedures or devices. Therefore, any adverse events related to treatment by this specialist would be considered a complication of the routine clinical care received by the patient while participating on the study. Any such complication would be managed by the interventional pain specialist, and the patients' oncology care team. That said, if a patient suffers a serious complication as the result of a pain procedure received while a participant on this study (i.e. a complication that is life threatening, requires hospitalization or prolongation of existing hospitalization, results in significant disability, requires a surgical procedure, death, etc), the study team will notify the IRB within one week of the event. Furthermore, participants will be reminded that participation is voluntary and can be stopped at any time for any reason.

